Grade 2 (Symptomatic, not interfering with Activities of Daily Living)	CT scan with lung windows. Consider pulmonary function testing includes: spirometry, DLCO, and room air O ₂ saturation at rest. Consider a bronchoscopy with biopsy and/or BAL. Monitoring at each visit until return to \leq grade 1. Return to initial monitoring frequency if no recurrence.	Symptomatic only. Consider corticosteroids and/or other supportive therapy if symptoms are troublesome.	Rule out infection and consider interruption of Everolimus until symptoms improve to Grade \leq 1. Re-initiate Everolimus at one dose level lower. Discontinue Everolimus if failure to recover within \leq 28 days.
Grade 3 (Symptomatic, Interfering with Activities of Daily Living. O ₂ indicated)	CT scan with lung windows and pulmonary function testing includes: spirometry, DLCO, and room air O ₂ saturation at rest. Monitoring at each visit until return to \leq grade 1. Return to initial monitoring frequency if no recurrence. Bronchoscopy with biopsy and/or BAL is recommended.	Consider corticosteroids if infective origin is ruled out. Taper as medically indicated.	Rule out infection and interrupt Everolimus until symptoms improve to Grade \leq 1. Consider re-initiating Everolimus at one dose level lower (approximately 50% lower than the dose previously administered depending on individual clinical circumstances) Discontinue Everolimus if failure to recover within \leq 28 days. If toxicity recurs at Grade 3, consider discontinuation
Grade 4 (Life-threatening, ventilatory support indicated)	CT scan with lung windows and required pulmonary function testing, if possible, includes: spirometry, DLCO, and room air O ₂ saturation at rest. Monitoring at each visit until return to \leq grade 1. Return to initial monitoring frequency if no recurrence. Bronchoscopy with biopsy and/or BAL is recommended if possible.	Consider corticosteroids if infective origin is ruled out. Taper as medically indicated.	Rule out infection and discontinue Everolimus.

Addendum 8: Action to be taken for positive baseline hepatitis B results

Test	Result	Result	Result	Result	Result
HBV-DNA	+	+ or -	-	-	-
HBsAg	+ or -	+	-	-	-
HBsAb	+ or -	+ or -	+ and no prior HBV vaccination	+ or -	- or + with prior HBV vaccination
HBcAb	+ or -	+ or -	+ or -	+	-
Recommendation	Prophylaxis treatment should be started 1-2 weeks prior to first dose of study drug. Monitor HBV-DNA approximately every 4 weeks		No prophylaxis Monitor HBV-DNA approximately every 4 weeks		No specific action

Antiviral prophylaxis therapy should continue for at least 4 weeks after last dose of study drug.

For patients who have already received study drug prior to the approval of Protocol Version date February 18, 2014, HBV-DNA testing will be performed at the patient's next visit, and the result will be regarded as baseline. Any action for positive hepatitis results will then proceed as detailed in the table above.

Addendum 9: Guidelines for management of hepatitis B

HBV reactivation (with or without clinical signs and symptoms)*	

For patients with baseline results:
 
Positive HBV-DNA OR positive HBsAg
 
-----
 
reactivation is defined as: [Increase of 1 log in HBV-DNA relative to baseline HBV-DNA value OR new appearance of measurable HBV-DNA]
 
AND
 
ALT elevation x 5 ULN
	
Treat: Start a second antiviral AND Interrupt study drug administration until resolution: \leq grade 1 ALT (or baseline ALT, if $>$ grade 1) and \leq baseline HBV-DNA levels
 
If resolution occurs within \leq 28 days study drug should be re-started at one dose lower, if available. If the patient is already receiving the lowest dose of study drug according to the protocol, the patient should restart at the same dose after resolution. Both antiviral therapies should continue at least 4 weeks after last dose of study drug.
 
If resolution occurs $>$ 28 days Patients should discontinue study drug but continue both antiviral therapies at least 4 weeks after last dose of study drug.

For patients with baseline results:
 
Negative HBV-DNA and HBsAg AND Positive HBs Ab (with no prior history of vaccination against HBV), OR positive HBc Ab
 
-----
 
reactivation is defined as: New appearance of measurable HBV-DNA
	
Treat : Start first antiviral medication AND Interrupt study drug administration until resolution: \leq baseline HBV-DNA levels
 
If resolution occurs within \leq 28 days study drug should be re-started at one dose lower, if available. If the patient is already receiving the lowest dose of study drug according to the protocol, the patient should restart at the same dose after resolution. Antiviral therapy should continue at least 4 weeks after last dose of study drug.

If resolution occurs > 28 days Patients should discontinue study drug but continue antiviral therapy at least 4 weeks after last dose of study drug.

- * All reactivations of hepatitis B are to be recorded as grade 3 (CTCAE v 3.0 Metabolic Laboratory/Other: Viral Re-activation), unless considered life threatening by the investigator; in which case they should be recorded as grade 4 (CTCAE v 3.0 Metabolic Laboratory/Other: Viral Re-activation). Date of viral reactivation is the date on which **both** DNA and ALT criteria were met (e.g. for a patient who was HBV-DNA positive on 01-JAN-10 and whose ALT reached $\geq 5 \times$ ULN on 01-APR-10, the date of viral reactivation is 01-APR-10).

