Co-administration with strong inhibitors of CYP3A4 (e.g., ketoconazole, itraconazole, ritonavir) or P-glycoprotein (PgP) should be avoided.

Co-administration with moderate CYP3A4 inhibitors (e.g., erythromycin, fluconazole) or PgP inhibitors should be used with caution. If patient requires co-administration of moderate CYP3A4 inhibitors or PgP inhibitors, reduce the dose of everolimus to half the currently used dose. Additional dose reductions to every other day may be required to manage toxicities. If the inhibitor is discontinued the everolimus dose should be returned to the dose used prior to initiation of the moderate CYP3A4/PgP inhibitor after a washout period of 2 to 3 days.

Seville orange, star fruit, grapefruit and their juices affect P450 and PgP activity. Concomitant use should be avoided.

Addendum 2: Inducers of CYP3A4 and/or PgP

If patients require co-administration of a strong CYP3A4 inducer, consider doubling the daily dose of Afinitor (based on pharmacokinetic data), using increments of 5 mg or less. This dose of Afinitor is predicted to adjust the AUC to the range observed without inducers. However, there are no clinical data with this dose adjustment in patients receiving strong CYP3A4 inducers. If the strong inducer is discontinued, consider a washout period of at least 3 to 5 days (reasonable time for significant enzyme de-induction), before the Afinitor dose is returned to the dose used prior to initiation of the strong CYP3A4 inducer.

This dose adjustment of everolimus is intended to achieve similar AUC to the range observed without inducers. However, there are no clinical data with this dose adjustment in patients receiving strong CYP3A4 inducers. If the strong inducer is discontinued the everolimus dose should be returned to the dose used prior to initiation of the strong CYP3A4/PgP inducer.

Addendum 3: Clinically relevant drug interactions: substrates, inducers, and inhibitors of isoenzyme CYP3A

SUBSTRATES	
Antibiotics: Clarithromycin, erythromycin, telithromycin	Calcium channel blockers: Amlodipine, diltiazem, felodipine, lercanidipine, nifedipine, nisoldipine, nitrendipine, verapamil
Anti-arrhythmics: Quinidine	HMG CoA reductase inhibitors: Cerivastatin, lovastatin, simvastatin
Benzodiazepines: Alprazolam, diazepam, midazolam, triazolam	Steroid 6beta-OH: estradiol, hydrocortisone, progesterone, testosterone

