Immune modulators: Cyclosporine, tacrolimus (FK506)	Miscellaneous: Alfentanil, aprepitant, aripiprazole, buspirone, cafergot, caffeine, cilostazol, cocaine, codeine-N-demethylation, dapsone, dexamethasone, dextromethorphan, docetaxel domperidone, eplerenone, fentanyl, finasteride, Gleevec/imatinib, haloperidol, irinotecan, LAAM, lidocaine, methadone, nateglinide, ondansetron, pimozide, propranolol, quetiapine, quinine, risperidone, salmeterol, sildenafil, sirolimus, sorafenib, sunitinib, tamoxifen, taxol, terfenadine, torisel, trazodone, vincristine, zaleplon, ziprasidone, zolpidem
HIV Antivirals: Indinavir, nelfinavir, ritonavir, saquinavir	
Prokinetic: Cisapride	
Antihistamines: Astemizole, chlorpheniramine, terfenadine	
INDUCERS	
Strong inducers: avasimibe, carbamazepine, mitotane, phenobarbital, phenytoin, rifabutin, rifampin (rifampicin), St. John's wort (hypericum perforatum)	

Moderate inducers:

bosentan, efavirenz, etravirine, genistein, modafinil, nafcillin, ritonavir, [talviraline], thioridazine, tipranavir

Weak inducers:

amprenavir, aprepitant, armodafinil (R-modafinil), bexarotene, clobazam, danshen, dexamethasone, Echinacea, garlic (allium sativum), gingko (ginkgo biloba), glycyrrhizin, methylprednisolone, nevirapine, oxcarbazepine, pioglitazone, prednisone, [pleconaril], primidone, raltegravir, rufinamide, sorafenib, telaprevir, terbinafine, topiramate, [troglitazone] , vinblastine

INHIBITORS**Clinically relevant drug interactions mediated by PgP**

PgP Substrates	PgP Inhibitors and PgP/CYP3A Dual Inhibitors	PgP Inducers
digoxin, fexofenadine, indinavir, vincristine, colchicine, topotecan, paclitaxel, talinolol, everolimus	amiodarone, azithromycin, captopril, carvedilol, clarithromycin, conivaptan, diltiazem, dronedarone, elacridar, erythromycin, felodipine, (GF120918), fexofenadine, fluvoxamine, ginko (ginkgo biloba), indinavir, itraconazole, lopinavir, (LY335979), mibepradil, milk thistle (silybum marianum), nelfinavir,	rifampin, St John's wort

Confidential

Clinical study protocol number: J1228

Page 49

Version Date: May 7, 2018

IRB study Number: NA_00067315

PgP Substrates	PgP Inhibitors and PgP/CYP3A Dual Inhibitors	PgP Inducers
	nifedipine, nitrendipine, (PSC833), paroxetine, quercetin, quinidine, ranolazine, rifampin, ritonavir, saquinavir, Schisandra chinesis, St John's wort (hypericum perforatum), talinolol, Telaprevir, telmisartan, ticagrelor, tipranavir, tolvaptan valspar, verapamil	

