Patients with a clinical history of stomatitis/mucositis/mouth ulcers and those with gastrointestinal morbidity associated with mouth/dental infections, irritation of esophageal mucosa e.g. gastroesophageal reflux disease (GERD) and pre-existing stomatitis/mucositis must be monitored even more closely. Patients should be

instructed to report the first onset of buccal mucosa irritation/reddening to their study physician immediately.

Stomatitis/oral mucositis/mouth ulcers due to Everolimus should be treated using local supportive care. Please note that investigators in earlier trials have described the oral toxicities associated with Everolimus as mouth ulcers, rather than mucositis or stomatitis. If your examination reveals mouth ulcers rather than a more general inflammation of the mouth, please classify the adverse event as such. The suggested paradigm for treatment of stomatitis/oral mucositis/mouth ulcers is as follows:

1. For mild toxicity (Grade 1), use conservative measures such as non-alcoholic mouth wash or salt water (0.9%) mouth wash several times a day until resolution.
2. For more severe toxicity (Grade 2 in which case patients have pain but are able to maintain adequate oral alimentation, or Grade 3 in which case patients cannot maintain adequate oral alimentation), the suggested treatments are topical analgesic mouth treatments (i.e., local anesthetics such as benzocaine, butyl aminobenzoate, tetracaine hydrochloride, menthol, or phenol) with or without topical corticosteroids, such as triamcinolone oral paste 0.1% (Kenalog in Orabase®).
3. Agents containing hydrogen peroxide, iodine, and thyme derivatives may tend to worsen mouth ulcers. It is preferable to avoid these agents.
4. Antifungal agents must be avoided unless a fungal infection is diagnosed. In particular, systemic imidazole antifungal agents (ketoconazole, fluconazole, itraconazole, etc.) should be avoided in all patients due to their strong inhibition of everolimus metabolism, thereby leading to higher everolimus exposures. Therefore, topical antifungal agents are preferred if an infection is diagnosed. Similarly, antiviral agents such as acyclovir should be avoided unless a viral infection is diagnosed.

Addendum 6: Management of hyperlipidemia and hyperglycemia

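### Addenda 1, 2, 3 and 5 give conflicting everolimus instructions for rifampin, St John's wort and fluconazole, and no rule says which one governs

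*Combined protocol and SAP*

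**What the plan says.** Section 3.3.2 (Concomitant therapy) requires patients to consult the investigator before taking any added medication, and points to Addenda 1 to 3 for interactions.

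- **Addendum 1, inhibitors.** "Co-administration with moderate CYP3A4 inhibitors (e.g., erythromycin, fluconazole) or PgP inhibitors should be used with caution". If such a drug is needed: "If patient requires co-administration of moderate CYP3A4 inhibitors or PgP inhibitors, reduce the dose of everolimus to half the currently used dose". Strong inhibitors of CYP3A4 or PgP are to be avoided.
- **Addendum 2, inducers.** "If patients require co-administration of a strong CYP3A4 inducer, consider doubling the daily dose of Afinitor". The increments are to be no more than 5 mg, and the addendum notes that clinical data for this adjustment are lacking.
- **Addendum 3, strong CYP3A inducers.** The list reads "avasimibe, carbamazepine, mitotane, phenobarbital, phenytoin, rifabutin, rifampin (rifampicin), St. John's wort (hypericum perforatum").
- **Addendum 3, PgP table.** The column for PgP inhibitors and dual PgP/CYP3A inhibitors includes "quinidine, ranolazine, rifampin, ritonavir, saquinavir, Schisandra chinesis, St John's wort (hypericum perforatum"). The separate PgP-inducer column names rifampin and St John's wort again.
- **Addendum 5, stomatitis.** On systemic antifungals: "ketoconazole, fluconazole, itraconazole, etc.) should be avoided in all patients due to their strong inhibition of everolimus metabolism".
- **Addendum 4.** After any dose change the trough level is redrawn 14 days later, within 3 days either way. Levels outside 3-15 ng/mL without toxicity above grade II lead to a step of 2.5 mg/day.

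**The concern.** An investigator whose patient needs one of these three drugs is sent to the addenda and finds two answers. For rifampin and St John's wort the answers point in opposite directions. For fluconazole one addendum permits use at a reduced everolimus dose and another rules it out.

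The trial's primary objective is the safety of this everolimus regimen. Section 6.0 counts as a failure any patient who cannot tolerate a stated minimum everolimus dose or has an unexpected hospitalization. The same events feed the safety stopping rule. Two clinicians reading the same addenda could start from opposite dose changes for the same co-medication. That is a patient-safety matter first. It also adds avoidable variation in exposure to a single-arm toxicity estimate.

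**Working it through.** The plan states no figure on this point, so there is nothing to reproduce. The check is a cross-reading, with one ratio.

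**Step 1. Map each drug to its classes and instructions.**

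| Drug | Class and place | Instruction that follows |
|---|---|---|
| Rifampin, St John's wort | PgP inhibitor (Addendum 3, PgP table) | Halve everolimus (Addendum 1) |
| Rifampin, St John's wort | Strong CYP3A inducer (Addendum 3) | Consider doubling everolimus (Addendum 2) |
| Fluconazole | Moderate CYP3A4 inhibitor (Addendum 1) | Use with caution; halve everolimus if needed |
| Fluconazole | Strong inhibitor (Addendum 5) | Avoid, for every patient |

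The double listing is not an artefact of text extraction. Both names stand in alphabetical position inside the inhibitor column and appear again in the inducer column.

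**Step 2. Size of the rifampin and St John's wort conflict.** Let d be the current everolimus dose.

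- Addendum 1 gives 0.5 × d.
- Addendum 2 gives 2 × d if doubling is chosen, and leaves d if it is considered and declined.
- Ratio if doubling is chosen: 2d / 0.5d = 4.
- Ratio if it is declined: d / 0.5d = 2.

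As an illustration at the 2.5 mg daily start in Section 3.3.1, halving gives 2.5 × 0.5 = 1.25 mg/day on average and doubling gives 2.5 × 2 = 5 mg/day. Tablets are swallowed whole and 2.5 mg is the smallest strength, so an average of 1.25 mg/day corresponds to 2.5 mg every other day. That is the dose named in Section 6.0's failure definition. The ratio is the same at any starting dose. It is a ratio of doses, not of exposures, because the co-medication itself changes exposure.

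**Step 3. Fluconazole.** The conflict is categorical. The two addenda differ on the potency class and on the action, so there is nothing to compute.

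**Step 4. What monitoring can do.** The redraw window after a dose change runs from 14 − 3 = 11 days to 14 + 3 = 17 days. A level outside 3-15 ng/mL would be seen then and could be corrected by titration. This comes after the first decision and does not say what that decision should be.

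**Step 5. PgP strength (secondary).** Addendum 1 separates strong PgP inhibitors (avoid) from PgP inhibitors generally (halve). The PgP table, as available for this review, carries no strength grading. The list under the CYP3A inhibitors heading is missing from the text reviewed, and that absence is not counted against the plan.

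**The case against.** The strongest case on the other side has four parts.

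- **Addendum 2 is permissive.** It says to consider doubling and admits that clinical data are lacking. This stands: only the halving is worded as a firm instruction, so four-fold is the gap only if doubling is chosen. The conflict remains, because declining to double still leaves a dose that Addendum 1 says to halve.
- **The fluconazole passages can be read together.** Addendum 5 is suggested stomatitis guidance and prefers topical agents, while Addendum 1 covers a patient who needs the drug. Avoidance by default with a reduced-dose exception would be workable, but the documents do not say this. Addendum 5 extends its statement to all patients, gives a general metabolic reason, and assigns a different potency.
- **Safeguards exist.** Section 3.3.2 requires consultation before any added medication, including over-the-counter products, which partly covers St John's wort. For invasive systemic fungal infection Section 3.2.5 already stops everolimus, so the fluconazole conflict concerns other uses. Both points narrow the exposure to error. Neither tells the consulted investigator which instruction applies.
- **Trough monitoring corrects errors.** It can, at about 11 to 17 days after a change, but not at the outset.

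A reader might infer more than the documents support:

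- *The interaction addenda are unusable as a whole.* The conflict is shown for three named drugs only.
- *Ritonavir is a further conflict.* Addendum 1 names it as a drug to avoid, its listing as a moderate inducer triggers nothing in Addendum 2, and known HIV is an exclusion.
- *Different sites will diverge.* The documents describe treatment at one cancer center.
- *A wrong change would go unseen for at least 14 days, or up to a month.* Addendum 4's redraw rule sets 11 to 17 days.
- *No PgP inhibitor can be classified.* Part of Addendum 3 is missing from the text reviewed, so this cannot be asserted.

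**Conclusion.** The point holds for rifampin, St John's wort and fluconazole. For the first two, the dose multipliers are 0.5 and 2, four-fold apart in opposite directions if doubling is chosen and two-fold apart if it is declined. For fluconazole, one addendum allows use with halving and another excludes use. No precedence rule resolves either case.

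The effect on the trial cannot be sized, because the documents do not say how many patients take these drugs. No claim is made that the toxicity estimate or the stopping rule would be materially altered. The case for correction rests on patient safety, on the addenda being the place where Section 3.3.2 sends the investigator, and on the low cost of the edit. It should be corrected, but it does not undermine the design. The PgP-strength question is only something for the sponsor to check against the complete Addendum 3.

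**What to change.** Reconcile Addenda 1, 2, 3 and 5 so that rifampin, St John's wort and fluconazole each lead to one instruction. This can be done in either of two ways:

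- list each drug only under the class that governs the everolimus action; or
- keep the pharmacological listings and add a rule stating which class takes precedence when a drug is in two.

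Give fluconazole the same potency class and the same action in Addenda 1 and 5. If Addendum 5 is meant to apply only to stomatitis care, or as a default with exceptions, say so there. The sponsor decides which instruction is kept; this review takes no view on that.

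Separately, confirm that the full Addendum 3 lets a reader tell strong PgP inhibitors from the rest. If it does not, mark the entries so that Addendum 1 can be applied.

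The cost is a text edit in the next amendment, with the sponsor-company review and IRB approval that Section 4 already requires. No visits, samples or staff are added.

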Clinical Experience of Everolimus in lymphoma: everolimus, an oral mTOR inhibitor, was tested at 10 mg qd in a Phase II study for patients with a number of different types of relapsed or refractory lymphomas – including aggressive, indolent and uncommon lymphomas^{32,33} . Thirty-seven (37) patients were treated in the aggressive lymphoma group - 20 (54%) with diffuse large B-cell (DLBC), 14 (38%) with MCL, 2 high grade, and 1 follicular grade III. Patients were eligible to enter if they had measurable disease and had met the following hematologic parameters: ANC \geq 1.0 x 109/L, platelets \geq 75.0 x 109/L and hemoglobin \geq 8 g/L. The median age was 72 years (range, 45-92). Patients had previously received a median of 4 prior therapies (range, 1-15). Prior stem cell transplant was allowed. The median treatment duration with Everolimus was 2 cycles (range 1-16+). The overall response rate was 32% (12/37; 95% CI: 20-49%) with 1 complete response and 11 partial responses. The overall response rate in the MCL patients was 29% (4/14); including one who received Everolimus for more than 14 cycles, while maintaining PR. The median time to progression for all 37 patients was 3.7 months (95% CI: 2.1 - 8.7). The median duration of response for the 12 responders was 5.5 months (95% CI: 2.3 - 9.2). Three patients are currently maintaining a response with a median of 10.5 months (2.9-15.6+ months). Everolimus was well tolerated. The incidence of grade 3 anemia, neutropenia, and thrombocytopenia in this heavily pretreated patient population was 11%, 16%, and 30%, respectively. Two patients developed grade 4 neutropenia. Grade 2 hypercholesterolemia occurred in 11%; grade 2 hyperglycemia in 16%; grade 3 hyperglycemia in 11% of the patients. One patient had grade 4 hypertriglyceridemia.

In the treatment of relapsed Hodgkin's disease, everolimus dosed at 10mg daily on a monthly cycle, the ORR was 47%. Ten of 19 patients had dose reductions or treatment delays. The median number of cycles at 10mg daily was five (range 1-20).

Everolimus serum levels are commercially available

- Quest Diagnostics (18883X) CPT code 80299, Mon-Fri
- Target trough concentrations 3-15 ng/mL

1.2 Hopkins experience of high-dose consolidative therapy with low grade B cell and Hodgkin's lymphoma.

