3.2.2. Inclusion Criteria

- Age \geq 18 years of age
- ECOG performance status \leq 2
- INR \leq 2
- Adequate renal and hepatic function defined as a serum creatinine \leq 2.0mg/dL, total bilirubin \leq 5mg/dL, and AST and ALT $<$ 2.5 ULN. • Platelet count \geq 75 x 10^9 /L
- Hemoglobin \geq 10mg/dL
- ANC \geq 3.0x 10^9 /L
- Fasting serum cholesterol \leq 300 mg/dL OR \leq 7.75 mmol/L and fasting triglycerides \leq 2.5 x ULN. NOTE: In case one or both of these thresholds are exceeded, the patient can only be included after initiation of appropriate lipid lowering medication.
- A willingness to use an accepted and effective method of birth control for sexually active women of childbearing potential during the study and for 8 weeks after the end of study drug treatment.
- Ability to sign informed consent.

Exclusion Criteria

- Patient who have previously received an mTor inhibitor
- Patients who are pre-terminal or moribund
- Patients currently receiving anticancer therapies or who have received anticancer therapies within 4 weeks of the start of Everolimus (including chemotherapy, radiation therapy, antibody based therapy, etc.)
- Uncontrolled diabetes mellitus as defined by HbA1c $>$ 8% despite adequate therapy. Patients with a known history of impaired fasting glucose or diabetes mellitus (DM) may be included, however blood glucose and antidiabetic treatment must be monitored closely throughout the trial and adjusted as necessary
- Chronic treatment with corticosteroids or other immunosuppressive agents. Topical or inhaled corticosteroids are allowed
- Patients who have received live attenuated vaccines within 1 week of start of Everolimus and during the study. Patient should also avoid close contact with others who have

received live attenuated vaccines. Examples of live attenuated vaccines include intranasal influenza, measles, mumps, rubella, oral polio, BCG, yellow fever, varicella and TY21a typhoid vaccines;

- Patients who have a history of another primary solid malignancy, with the exceptions of: non-melanoma skin cancer, and carcinoma in situ of the cervix, uteri, or breast from which the patient has been disease free for ≥ 3 years;
- Patients with a history of non-compliance to medical regimens or who are considered potentially unreliable or will not be able to complete the entire study;
- Patients with active bacterial or fungal infections requiring oral or intravenous antimicrobials are not eligible until resolution of the infection

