Reference: Internal Clinical Pharmacology Drug-drug interaction (DDI) memo, updated Oct. 2, 2011, 29-Oct-2012 which summarizes DDI data from three sources including the FDA's "Guidance for Industry, Drug Interaction Studies", the University of Washington's Drug Interaction Database, and Indiana University School of Medicine's Drug Interaction Table.

Addendum 4: Dose Modifications for abnormal serum drug concentrations without grade III/IV toxicities, grade \geq III toxicities (CTCAE version 4.0) except for stomatitis and lipid/hyperglycemia toxicities

- Patient will have regularly scheduled everolimus levels drawn throughout the study
- Everolimus is available in 2.5mg, 5mg and 10mg strengths
- The reference range for patients experiencing a <II common toxicity (CTCAE version 4.0) is 3-15ng/mL
- Anytime a dose is adjusted, repeat everolimus serum trough levels will be re-drawn 14 days (\pm 3 days) later. As clinically possible, all patients' other labs will be reset to match this new everolimus serum trough level schedule.
- Once everolimus is held due to high serum trough levels, everolimus should be held for 7 days before restarting at a lower dose level.
- During a treatment hold, everolimus levels will not be drawn once the serum trough level is less than 1.0.
- There is no limit on how long a patient can be on everolimus treatment hold. Labs will be monitored every two weeks while the patient is on hold.
- For patients >15 ng/mL or <3.0 ng/mL and not experiencing >II grade common toxicity, their dose will be adjusted by $+/-.2.5$ mg/day; lowest dose allowed is 2.5mg every 4 days. The study nurse will provide a calendar to patients when the dose level is 2.5 mg taken every 3 or 4 days
- If a patient on a schedule of 2.5 mg (QOD) or lower misses a dose, that dose should be made up.
- Non-hematologic grade \geq III CTCAE toxicities: hold drug until CTCAE toxicity is (I) but can be continued at grade 2 if the baseline values were within the range of grade 2 and restart at a dose level -2.5mg/day. Lowest dose allowed is 2.5mg every 4 days
- Grade 4 or 4 clinical failure – discontinue RAD001
- Recurrence of grade 4 toxicity after dose reduction – discontinue RAD001
- Hematologic grade \geq III CTCAE toxicity
 - Anemia
 - Hgb <8.0 g/dL: transfuse RBC; hold drug for 7 days or until Hgb >10 mg/dL (untransfused): whichever is longer. Restart at a dose - 2.5mg/day. Lowest dose allowed is 2.5mg every 4 days
 - Thrombocytopenia

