 - Platelets $< 50,000$: hold drug until platelet count is $>75,000$ and restart at a dose level -2.5mg/day. Lowest dose allowed is 2.5mg every 4 days

- Platelets <10,000: transfuse PLT: when platelet count is >75,000 (transfusion independent: at least 7 days). Restart at a dose level -2.5mg/day; lowest dose allowed is 2.5mg every 4 days
- Neutropenia:
 - ANC <1,000/mm³ hold drug (and rituximab) until ANC >1,500 and restart at a dose level -2.5mg/day. Lowest dose allowed is 2.5mg every 4 days
 - No adjustments will be made for lymphopenia
- Lowest dose allowed on protocol is 2.5mg every 4 days. If serum concentrations on this dosing schedule are >15ng/mL or if on this dosing schedule greater than grade II toxicities are experienced the patient will be taken off study. However, patients will be followed until toxicities return to grade 1 or baseline as appropriate.

Addendum 5: Management of stomatitis/oral mucositis/mouth ulcers

Management of stomatitis / oral mucositis / mouth ulcers

Adverse Drug Reaction	Severity	Afinitor Dose Adjustment and Management Recommendations
Stomatitis	Grade 1 (Minimal symptoms, normal diet)	No dose adjustment required. Manage with non-alcoholic or salt water (0.9%) mouth wash severaltimes a day.
	Grade 2 (Symptomatic but can eat and swallow modified diet)	Temporary dose interruption until recovery to grade ≤ 1 . Re-initiate Afinitor at the same dose. If stomatitis recurs at grade 2, interrupt dose until recovery to grade ≤ 1 . Re-initiate Afinitor at a lower dose. Manage with topical analgesic mouth treatments (e.g. benzocaine, butyl aminobenzoate, tetracaine hydrochloride, menthol or phenol) with or without topical corticosteroids (i.e. triamcinolone oral paste)*.
	Grade 3 (Symptomatic and unable to adequately eat or hydrate orally)	Temporary dose interruption until recovery to grade ≤ 1 . Re-initiate Afinitor at lower dose. Manage with topical analgesic mouth treatments (i.e. benzocaine, butyl aminobenzoate, tetracaine hydrochloride, menthol or phenol) with or without topical corticosteroids (i.e. triamcinolone oral paste)*
	Grade 4 (Symptoms associated with life-threatening consequences)	Discontinue Afinitor and treat with appropriate medical therapy.

* using agents containing alcohol, hydrogen peroxide, iodine, and thyme derivatives in management of stomatitis as they may worsen mouth ulcers.

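### Hemoglobin entry and restart limits are written as 10 mg/dL, very probably in error for 10 g/dL

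*Combined protocol and SAP*

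**What the plan says.** Three hemoglobin thresholds govern patients in this trial.

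- **Entry** (Section 3.2.2, Inclusion Criteria): "Hemoglobin \geq 10mg/dL".
- **Hold** (Addendum 4, anemia rule): "Hgb <8.0 g/dL: transfuse RBC", with everolimus stopped.
- **Restart** (same bullet of Addendum 4): "hold drug for 7 days or until Hgb >10 mg/dL (untransfused): whichever is longer", followed by a dose 2.5 mg/day lower.

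The anemia rule stands under the item "Hematologic grade \geq III CTCAE toxicity", together with rules for platelets and neutrophils. For platelets below 50,000 the instruction is "hold drug until platelet count is $>75,000$ and restart at a dose level -2.5mg/day". For ANC below 1,000/mm³ it is "hold drug (and rituximab) until ANC >1,500 and restart at a dose level -2.5mg/day".

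The only other numeric hemoglobin limit is in Section 1.1.3: "hemoglobin \geq 8 g/L". It describes who could enter an earlier everolimus study and is not a rule of this trial.

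**The concern.** The hold trigger is in g/dL, while the entry and restart limits are in mg/dL. The two units differ by a factor of 1000, so the restart limit as written lies far below the level that starts the hold. A recovery threshold has to sit above the trigger, or it does not require recovery.

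Two decisions depend on these limits: who may enter, and when a patient with severe anemia may go back on drug. Section 3.2.1 requires every inclusion criterion to be met and checked before enrollment, and Section 3.2.3 lists protocol violation among the reasons for taking a patient off study. Compliance is judged against the written text. A patient with hemoglobin 9 g/dL satisfies the entry criterion as written but fails the evident intent.

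**Working it through.** The check is a unit conversion and a comparison of order. The plan derives no figure here that could be reproduced.

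**Inputs**

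| Quantity | As written | Source |
|---|---|---|
| Hemoglobin, entry | at least 10 mg/dL | Section 3.2.2 |
| Hemoglobin, hold | below 8.0 g/dL | Addendum 4 |
| Hemoglobin, restart | above 10 mg/dL | Addendum 4 |
| Platelets, entry | at least 75 x 10⁹/L | Section 3.2.2 |
| Platelets, hold / restart | below 50,000 / above 75,000 | Addendum 4 |
| ANC, entry | at least 3.0 x 10⁹/L | Section 3.2.2 |
| ANC, hold / restart | below 1,000 / above 1,500 | Addendum 4 |

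**Step 1. Put hemoglobin on one scale** (1 g/dL = 1000 mg/dL).

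- Entry and restart limit: 10 / 1000 = 0.01 g/dL.
- Hold trigger: 8.0 x 1000 = 8000 mg/dL.
- Hold trigger relative to restart limit: 8000 / 10 = 800.

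**Step 2. Follow the literal rule.** A patient on an anemia hold already exceeds 0.01 g/dL when the hold begins. The hemoglobin part of the condition is therefore met at once. What remains is the 7-day minimum and the untransfused requirement, which is a separate condition for someone who has just received red cells. A patient still below 8.0 g/dL would meet the written hemoglobin level. Every candidate likewise meets the written entry limit.

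**Step 3. Compare with the other blood-count rules** (restart limit divided by hold limit).

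- Platelets: 75,000 / 50,000 = 1.5.
- ANC: 1,500 / 1,000 = 1.5.
- Hemoglobin as written: 0.01 / 8.0 = 0.00125.
- Hemoglobin if g/dL is meant: 10 / 8.0 = 1.25.

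The protocol sets no common ratio, so the exact values matter little. What matters is whether the ratio is above or below 1. Both other rules require recovery above the hold level, and hemoglobin does so only in g/dL, where restart lies 10 - 8.0 = 2 g/dL above the trigger.

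**Step 4. Compare entry with restart.** For platelets the two limits are the same (75 x 10⁹/L is 75,000 per mm³), just as hemoglobin uses 10 in both places. This is weak support, because ANC does not follow it: entry is 3.0 x 10⁹/L, or 3,000 per mm³, against a restart level of 1,500.

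**Step 5. Rule out a reading error in the PDF.** The mg/dL unit appears in two separate places with different spacing, and g/dL was read correctly within the same Addendum 4 bullet. A conversion fault is unlikely. In Section 3.2.2, creatinine, bilirubin and cholesterol are properly given in mg/dL close by, which may be how the unit slipped in.

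**The case against.** The strongest reply is that the slip corrects itself. The Addendum 4 bullet opens with a trigger in g/dL, so the intended scale is on the page, and no clinician could act on a hemoglobin of 10 mg/dL. On that view no patient would be enrolled, held or restarted differently, and the point is copy-editing. This largely stands as a judgment of weight, and it is why the point is rated minor. It does not make the text right, since eligibility and dosing compliance are documented against the written limits.

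A second reply is that the supporting pattern is weaker than it looks. Any hemoglobin value above 8.0 g/dL would put restart above hold, so the ordering does not by itself single out 10, and the match between entry and restart limits fails for ANC. Both observations are correct. The case for g/dL rests on the trigger in the same bullet and on the number 10 as printed. The sponsor should confirm the value.

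**Conclusion.** The concern holds. Both the entry limit and the restart limit for hemoglobin carry a unit that is wrong by a factor of 1000, and nothing elsewhere in the document corrects them. Literally applied, the entry criterion screens out no one and the restart level has no effect.

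That 10 g/dL is meant is an inference, though a strong one. It assumes that the printed number is right and only the unit is wrong. The likely practical effect is small, because staff would very probably read g/dL. No sample size, stopping rule or analysis depends on it. This is a minor correction, held with high confidence.

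**What to change.** After the sponsor confirms the intended value:

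- Section 3.2.2: state the hemoglobin criterion as at least 10 g/dL.
- Addendum 4, anemia rule: state the restart level as above 10 g/dL, untransfused, and keep the 7-day minimum.

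The cost is a unit correction in two lines, with no change to design, sample size or analysis.
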